7.4 Unanticipated Adverse Events

An unanticipated adverse event is an AE for which the nature or severity are not consistent with the applicable product information (refer to IFU and on-label use). Unanticipated adverse events are to be reported to the study sponsor, each reviewing IRB, and the FDA, no later than ten (10) days after the date the adverse event was discovered. The coordinating center will be responsible for the communication with the regulatory bodies.

7.5 Anticipated Adverse Events

An anticipated adverse event is an AE for which the nature and severity are consistent with the applicable product information (e.g. Package insert/summary of product characteristics for an approved product). This term relates only to the treatment, not the patient's underlying condition.

7.6 Unanticipated Adverse Device Effects

Unanticipated adverse device effects (UADE) are defined as any serious adverse effect on health or safety or any life-threatening problem or death caused by, or associated with, a device, if that effect, problem, or death was not previously identified in nature, severity, or degree of incidence in the investigational plan or application (including a supplementary plan or application), or any other unanticipated serious problem associated with a device that relates to the rights, safety, or welfare of study patients.

All UADEs must be reported to the FDA immediately upon the Investigator's awareness of the event. The AE Forms of the CRF must be completed within 7 working days for all UADEs. The Investigator is also responsible for notifying his/her IRB of all UADEs occurring at his/her site no later than 10 days after the investigator first learns of the effect (and any additional information as required by EC/IRB or local regulations). All UADE adverse events must be followed until resolution or until a stable clinical endpoint is reached. All required treatments and outcomes of the UADE adverse event must be recorded.

7.7 Adverse Event Follow-up

All adverse events occurring within the follow-up period (whether serious, non-serious, unanticipated, or anticipated) will be monitored and documented according to the follow-up. To be compliant with ethical and regulatory principles, treatment-related SAEs that occur after follow-up is completed (outside the protocol) and are assessed by the investigator as "unanticipated" must be updated to the FDA via the MAUDE reporting system in accordance with FDA regulations

8.0 DATA MONITORING AND QUALITY CONTROL

8.1 Case Report Forms (CRFs)

Case report forms (CRFs, see addendum) will be generated, based on the investigational plan. An electronic clinical trial management system (RedCap, Vanderbilt U, TN) will be used to collect all patient data during the trial by the data coordinators or their designee. Data will be collected in a paper form or in electronic format and entered into the electronic clinical trial management system. Paper forms will be kept in a secure location and only accessible to the data coordinator or investigator.

8.2 Data Reporting

The Investigator or his/her designee is responsible for recording all data from the trial onto the CRFs. Completed CRFs will be reviewed at regular intervals throughout the trial. To this end, the Investigator must permit inspection of the trial paper files and patient CRFs by such representatives and/or responsible government agencies including the FDA or DMSB.

8.3 Data Review

All CRFs will be thoroughly reviewed and all missing or unclear data will be adjudicated by the investigator or his designee throughout the study. Any data which has not been collected or is unavailable will also be noted. For purposes of safety review the DMSB will have access to all necessary safety and event data.

8.4 Records

Records to be maintained by the site investigator include:

- Correspondence
 - IRB Correspondence (incl. IRB approval)
 - Sponsor correspondence
 - General correspondence
- Study documents
 - Clinical protocol including all amendments
 - Informed consent and HIPAA authorization
 - Sample case report form (database)
 - Instruction for use (device)
 - Statement of investigator
 - Laboratory certifications
 - Laboratory reference ranges
- Study tracking logs
 - Subject logs
 - Adverse events and unanticipated adverse device effects log
 - Device accountability log
 - Monitoring log
- Research personnel
 - PI (site PI):
 - curriculum vitae
 - current medical license
 - human subject protection training document
 - conflict of interest or financial disclosure form(s)
 - Sub-PI:
 - curriculum vitae
 - current medical license
 - human subject protection training document
 - conflict of interest or financial disclosure form(s)
 - Signature and delegation of responsibility log
- For sites that are using a local IRB
 - IRB compliance document (FWA)
- Bi-annual reports to the FDA

The following records must be maintained for each patient enrolled in the trial:

- Signed Patient Informed Consent Form;
- All completed CRFs;
- Supporting documentation of any complications or serious adverse events.

Investigator's Final Report

Upon completion or termination of the HOVER study, the overall Principal Investigator must submit a final written report to the FDA and the IRB. The report must be submitted within 3 months (90 days) of completion or termination of the trial.

Protocol Deviations/Violations

The investigator will not deviate from the protocol without the prior written approval of the IRB except where necessary to eliminate an apparent immediate hazard.

9.0 ETHICAL AND REGULATORY CONSIDERATIONS

9.1 Role of the Sponsor investigator

The sponsor investigator has the overall responsibility for the conduct of the study, including assurance that the study meets the regulatory requirements of the appropriate regulatory bodies. In this study, the sponsor will have certain direct responsibilities and may delegate other responsibilities to the study coordinator or other investigators.

9.2 General Duties

The Sponsor's general duties consist of submitting the appropriate regulatory applications, obtaining IRB or Ethics Committee approval, selecting investigators, ensuring proper clinical site monitoring and ensuring study patient informed consent is obtained. Based on data collected from the study, the sponsor will prepare written progress reports and a final report.

9.3 Selection of Investigators

The Sponsor will select qualified investigators, obtain a signed Investigator's Agreement and provide the investigators with the information necessary to conduct the study.

9.4 Monitoring (See also Monitoring Plan)

The Sponsor or its designee, will monitor the study to ensure compliance with the protocol and the Investigator's Agreement. The sponsor will evaluate circumstances where an investigator deviates from the clinical protocol and will retain the right to remove the investigator from the study. The Sponsor will review significant new information, including unanticipated adverse events and ensure that such information is provided to the DMSB, study investigators and to all reviewing IRB/ECs.

9.5 Supplemental Applications

As appropriate, the principal investigator will submit changes in the Investigational Plan to the regulatory authority. The principal investigator will submit all changes in the Investigational Plan to investigators to obtain IRB re-approval.

9.6 Maintaining Records

The Sponsor will maintain copies of correspondence, all data, adverse device effects and other records related to the clinical trial as appropriate.

9.7 Submitting Reports

The Sponsor will submit all reports required by the appropriate regulatory authorities, including unanticipated adverse device effects, withdrawal of IRB approval, current investigators list, annual progress reports, final reports protocol violations.

9.8 Informed Consent

All study patients must personally provide written informed consent. Copies of the informed consent form must be maintained for the duration of the study. One copy will reside in the medical chart, one copy will be provided to the patient, and the original resides in the regulatory binder on site. The IRB approval letter for the study will also be maintained. The study patient has been informed of the nature

of the study, agrees to its provisions and has provided written informed consent as approved by the Institutional Review Board (IRB) of the respective clinical site.

10.0 STUDY DATA REPORTING AND PROCESSING

10.1 Data Processing and Quality Control

The online database will reside on a central server accessible through the Internet. It will be password protected and available only to the investigators and study personnel. The database will be protected by whole disk encryption.

10.2 Data Entry

The data entry is performed by study personnel on a secured and dedicated website. All data entered is subjected to data type verification.

10.3 Data Cleaning

All CRFs will be subjected to initial inspection for omitted data, data inconsistencies, and deviations. The resolution of data inconsistencies will be done by the investigators or other data management specialists.

10.4 Data Editing

Corrections to the CRFs will be made by the research coordinator, and approved by the investigator or designee.

10.5 Confidentiality and Protection of Study Files

Passwords will be issued to appropriate data management personnel to ensure confidentiality and protection of the data by allowing variable levels of access to the computer system.

		____/____ ____:____ — ____:____	 1 Ongoing  2 Resolved  3 Pt. Died	____/____ ____:____ — ____:____	 1 Mild  2 Moderate  3 Severe  4 SAE*	 0 NO  1 YES**	 0 NO  1 Stopped temporarily  2 Stopped Permanently	 1 Unlikely  2 Possibly  3 Probably	
		____/____ ____:____ — ____:____	 1 Ongoing  2 Resolved  3 Pt. Died	____/____ ____:____ — ____:____	 1 Mild  2 Moderate  3 Severe  4 SAE*	 0 NO  1 YES**	 0 NO  1 Stopped temporarily  2 Stopped Permanently	 1 Unlikely  2 Possibly  3 Probably	
		____/____ ____:____ — ____:____	 1 Ongoing  2 Resolved  3 Pt. Died	____/____ ____:____ — ____:____	 1 Mild  2 Moderate  3 Severe  4 SAE*	 0 NO  1 YES**	 0 NO  1 Stopped temporarily  2 Stopped Permanently	 1 Unlikely  2 Possibly  3 Probably	

Describe:
 <hr/> 
If event is SAE then submit AE form to medical reviewer within 24 hours. **If YES and device related, complete UADE form
									

UNANTICIPATED ADVERSE DEVICE EFFECT FORM

1. Date form completed		— / — / — —	MO	DAY	4-Digit YEAR			
2. Date and time of onset:		— / — / — —	MO	DAY	4-Digit YEAR	— : —	(Military time)	
3. Has event resolved?  YES  NO		If YES, Date/Time resolved: — / — / — —						
		MO	DAY	4-Digit YEAR	— : —	(Military time)		
4. Relationship to study device: (choose one)		 NOT related	 Probably related	 Unknown				
		 Possibly related	 Definitely related					
If related, (1, 2 or 3) then specify Serial ID# for device _____								
5. In your opinion, is this a UADE*  YES  NO								
6. Action taken (Check all that apply)		 YES  NO None						
		 YES  NO Medication, specify: _____						
		 YES  NO Surgery, specify _____						
		 YES  NO Other, specify _____						
7. Severity (Check one)		 Mild  Moderate  Severe  Life threatening						
8. Outcome (Check all that apply)								
YES	NO			YES	NO			
		A. Continuing WITHOUT treatment				E. Recovered WITHOUT treatment		
		B. Continuing WITH treatment				F. Recovered WITH treatment		
		C. Continuing with sequelae, specify: _____				G. Patient expired (attach copy of autopsy or death summary)		
		D. Temporary disability				H. Permanent disability		
9. Description of adverse effect: _____								
* An Unanticipated Adverse Device Effect (UADE) is any serious adverse effect on health or safety, or any life-threatening problem or death caused by or associated with this device, if that effect, problem, or death is not identified in nature, severity, or degree of incidence in this Investigational Study; or any other unanticipated serious problem associated with this device that relates to the rights, safety or welfare of the subjects. UADEs must be reported to the principal investigator and the IRB within 10 working days.								
I verify that the form completed for this UADE is accurate and representative of the data available in source documentation.								
Investigator's signature				Date — / — / — — MO DAY 4-Digit YEAR				

APPENDIX A: HOVER ECHO PROTOCOL

-left parasternal long axis

- Coronary sinus dimension
- proximal RVOT dimension

-left parasternal RV inflow

[figure not shown]
- 2D: distinguish functional vs. degenerative/rheumatic/carcinoid TR etiologies
- Color Doppler:
 - identify TR etiology
 - help identify TR severity
- Vena contracta: >7 mm is in favor of severe TR; <6mm - non-severe TR
- Continuous wave Doppler
 - assess density/contour of TR signal
 - measure RVSP

-left parasternal RV outflow

- distal RVOT dimension
- pulsed wave/continuous Doppler of RVOT (RVOT VTI)
- RV stroke volume

[figure not shown]
-left parasternal short axis

- 2D: distinguish functional vs. degenerative/rheumatic/carcinoid TR etiologies
- 2D: proximal/distal RVOT dimension

[figure not shown]

- Color Doppler:
 - identify TR etiology
 - help identify TR severity
- Continuous wave Doppler
 - assess density/contour of TR signal
 - measure RVSP
- pulsed wave/continuous Doppler of RVOT (RVOT VTI)
- RV stroke volume

[figure not shown]
-Apical 4 chamber

- 2D: distinguish functional vs. degenerative/rheumatic/carcinoid TR etiologies
- 2D: Measure tenting area and coaptation distance
- Coronary sinus dimension (apical 4 chamber tilted inferiorly)
- RV TAPSE (*obtained from whichever apical view with best alignment)
- Color Doppler:
 - identify TR etiology
 - help identify TR severity
- PISA:
 - lower Nyquist limit to 15-40 cm/s
 - EROA \geq 40 mm² or Regurgitant Volume \geq 45 mL suggestive of severe TR
- Pulsed Doppler of TV inflow
 - get E/A with sample volume at TV tips; E \geq 1 m/s suggests severe TR
- Continuous wave Doppler
 - assess density/contour of TR signal
 - measure RVSP
 - RV dp/dt (from best TR signal)
- RV lateral tricuspid annulus tissue Doppler (*obtained from whichever apical view with best alignment)

[figure not shown]

-RV Tei index (tissue Doppler) (*obtained from whichever apical view with best alignment)

-RA volume index (via area-length or method of discs)

-RV-focused apical 4-chamber

[figure not shown]

RV focused apical 4-chamber

[figure not shown]
-RV basal and mid dimensions

Echocardiographic imaging	Recommended methods	Advantages	Limitations
RV linear dimensions (inflow)*	

 
 • Basal RV linear dimension (RVD1) = maximal transversal dimension in the basal one third of RV inflow at end-diastole in the RV-focused view • Mid-cavity RV linear dimension (RVD2) = transversal RV diameter in the middle third of RV inflow, approximately halfway between the maximal basal diameter and the apex, at the level of papillary muscles at end-diastole. 	
 • Easily obtainable • Simple • Fast • Wealth of published data 	
 • RV size may be underestimated due to the crescent RV shape • RV linear dimensions are dependent on probe rotation and different RV views; in order to permit inter-study comparison, the echocardiography report should state the window from which the measurement was performed.

[figure not shown]
-RVEF (2D planimetry of end-sys and end-dias area) *consider contrast microbubble contrast

-RV global longitudinal strain

-RV modified apical 4-chamber

-subcostal views with IVC/SVC and R/L hepatic vein visualization

- hepatic vein flow reversal
- Bubble study – looking at reflux in hepatic veins
- measure IVC flow and hepatic vein dimension
- measure SVC flow and dimensions
- measure distance between hepatic vein os and IVC-RA junction
- measure RV free wall thickness
- (post CAVI) identify position of Edwards-Sapien valve in relation to hepatic vein os and IVC-RA junction**

-3D TTE of TV (obtained in any view with greatest TV visualization)

- distinguish functional vs. degenerative/rheumatic/carcinoid TR etiologies
- Measure tenting area and coaptation distance
- Color Doppler:
 - identify TR etiology
 - help identify TR severity
- Vena contracta: EROA > 75 mm² by 3D Color – severe TR

-3D TTE of RV

- quantify RV volume with full volume acquisition

References:

Recommendations for Cardiac Chamber Quantification by Echocardiography in Adults: An Update from the American Society of Echocardiography and the European Association of Cardiovascular Imaging, JASE Jan 2015; 28:1-39.

European Association of Echocardiography recommendations for the assessment of valvular regurgitation. Part 2: mitral and tricuspid regurgitation (native valve disease) European Journal of Echocardiography (2010) 11, 307-332

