2.0 PROJECT PLAN

2.1 Rationale for Study

Severe TR is characterized by right heart congestion and volume overload¹⁵. Non-surgical treatment for TR relies on the administration of increasing doses of diuretic therapy to promote diuresis and volume contraction. However, many patients go on to become refractory to chronic diuretics over time. This is in part to the effects on chronic right heart congestion on the kidney. Based on previous studies, we believe that protection of the hepatic and renal veins with a one-way valve from the transmitted TR will allow for continued diuresis, and improvement in symptoms. Although CAVI has shown improvements in right heart congestion in a small series of patients, several questions remain. Previous studies have not clearly excluded TR that can occur with pulmonary arterial hypertension (PAH.) As 2/3 of the regurgitant flow from tricuspid regurgitation is directed to the IVC, the effects of redirection of this flow to the SVC are unknown. The degree of TR can be sensitive to changes in pre-load. It remains unclear if improvement in right heart congestion may therefore also affect degree of TR and indices of right ventricular (RV) function. Finally, the durability of the procedure beyond the intermediate term (6 months) is not well characterized. To help clarify these issues, we have created the Heterotopic Implantation Of the Edwards Sapien 3 Transcatheter Aortic Valve in the Inferior VEna cava for the treatment of severe Tricuspid Regurgitation study.

2.2 Design:

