This is a prospective multi-center, non-blinded (open label), non-randomized safety and feasibility study of the heterotopic implantation of the Edwards Sapien 3 valve in the inferior vena cava for the treatment of severe tricuspid regurgitation in patients who are inoperable or at a very high surgical risk for tricuspid valve replacement. Patients enrolled will have severe TR and cardiac symptoms of right heart congestion in whom conventional tricuspid valve surgery (TVR) would be associated with high risk. Severe TR is defined by a vena contracta width > 7mm OR evidence of systolic hepatic vein flow reversal OR visible tricuspid valve coaptation defect + dense/triangular continuous wave with early peaking as assessed by continuous wave signal AND a very large central jet or eccentric wall impinging jet as assessed by color flow. ¹⁶. All patients must be on diuretics with documented evidence of continued venous congestion, such as lower extremity or abdominal wall edema.

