2.3 Statistical Analysis

A total of up to 15 patients will be enrolled. Due to the lack of preliminary data as well as exploratory nature of the study, no sample size and power analyses were performed. We expect to screen approximately 45 patients to enroll up to 15 eligible patients into this trial.

All clinically relevant baseline and follow-up data will be tabulated. Means (SDs), medians (ranges), and 95% confidence intervals will be reported for continuous variables and frequencies, percentages, and 95% confidence intervals for categorical variables. Specifically, each of the two primary endpoints (the procedural success at 30-days and the composite binary response variable at 6-months) will be summarized using both a point estimate and its exact confidence interval based on a binomial distribution. Other binary safety and efficacy secondary endpoints will be analyzed similarly. Continuous secondary endpoints (e.g., hemodynamics data) will be reported using descriptive summary statistics as well as a point estimate and its confidence interval based on a normal distribution assumption. The changes from baseline to each follow-up timepoint will additionally be evaluated using the McNemar matched pairs test for dichotomous variables and the t-test for continuous variables. In the presence of distributional non-normality, the Wilcoxon signed rank test will be used instead of the t-test. Data transformations such as log or square-root may also be considered. The analyses of NYHA functional classification will involve comparison of the baseline and post-operative (at each timepoint) functional class and determination of the percentages of patients improving, not changing, or worsening at each postoperative timepoint. The same principle will be applied to quality of life score (KCCQ) and 6-minute walk distance. Although this is an exploratory analysis, we anticipate 50% of patients will demonstrate improvement in one of the three pre-specified components of the primary efficacy outcome.

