- Acute Kidney Injury (VARC-2)
- Major Vascular Complication (VARC-2)

Secondary efficacy endpoints include:

- Assessment of improvement of LE edema by the Villalta Score²⁵. A 3.1 point improvement in this scale was associated with improved quality of life²⁶.

Besides the above formal secondary endpoints, we will monitor for the following throughout the trial:

- Deep Vein/IVC thrombosis or pulmonary embolism
- Improvement in grades of tricuspid regurgitation as assessed by echocardiogram
- Changes in TAPSE by echocardiogram for RV function
- Pleural effusions
- Additional quality questionnaires to assess for changes in ascites (EORTC QLQ-C30²⁷ and ESAS-AM²⁸). A 10-point change in mean score in the QLQ-C30 has been shown to be a meaningful response (O'Connor R. Measuring Quality of Life in Health Churchill Livingstone: Philadelphia; 2004). A decrease of 1.25 points in the ESAS-AM has been shown to correlate with symptom improvement after paracentesis²⁸.

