3.3 Eligibility Process

All patients with severe tricuspid regurgitation and symptoms who are high risk or inoperable will be screened for study inclusion. Patients must have all inclusion criteria, and be free from all exclusion criteria. Screening and enrollment logs will be maintained. Reasons for screen failures will be documented. The full description and timing of screening tests can be found in Table 1.

3.4 Participant Inclusion Criteria:

In order to be eligible to participate in this study, an individual must meet all of the following criteria

1. Patients must be at least 21 years old.
2. The patient must have severe, symptomatic (ACC/AHA Stage D symptoms) tricuspid regurgitation (TR) as assessed by 2D echocardiogram with evidence of peripheral and central venous congestion (specifically lower extremity edema and abdominal ascites requiring diuretics.)
3. The patient must be evaluated by a “heart team” of physicians including an interventional cardiologist, cardiothoracic surgeon, heart failure specialist, and imaging specialist, and presented for review at a local multi-disciplinary conference. By consensus, the heart team must agree (and verify in the case review process) that valve implantation will likely benefit the patient.
4. The heart team must agree that medical factors preclude operation, based on a conclusion that the probability of death or serious, irreversible morbidity exceeds the probability of meaningful improvement. Also, other factors which may increase the patients perceived surgical risk for inclusion in the trial will be clearly delineated if they are present. These include, but are not limited to the following as defined by VARC 2: Frailty, Hostile chest, porcelain aorta, IMA or other critical conduit crossing the midline or adherent to the posterior table of sternum, severe right ventricular (RV) dysfunction. The surgeons' consultation notes shall specify the medical or anatomic factors leading to that conclusion. At least one of the cardiac surgeon assessors must have interviewed and examined the patient.
5. The study patient provides informed consent and agrees to comply with all required post-procedure follow-up visits, including annual visits up to 5 years.
6. Mean diameter of the IVC at the right atrial junction or superior most hepatic vein $\leq 30.5\text{mm}$

3.5 Participant Exclusion Criteria:

Patient or Subject will be excluded from the study if any of the following conditions are present:

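### TR is monitored only as improvement in grade, a measure with a ceiling at entry and no defined scale; none of the continuous TR measurements in Appendix A is named for follow-up

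*Combined protocol and SAP*

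**What the plan says.** - **The question.** Section 2.1 lists degree of TR among the matters the study should help to clarify: "It remains unclear if improvement in right heart congestion may therefore also affect degree of TR".
- **Entry.** Section 3.4, inclusion criterion 2: "The patient must have severe, symptomatic (ACC/AHA Stage D symptoms) tricuspid regurgitation (TR) as assessed by 2D echocardiogram". Section 2.2 gives the definition, which begins "Severe TR is defined by a vena contracta width > 7mm OR evidence of systolic hepatic vein flow reversal" and continues with further alternatives. Section 2.2.2 has the coordinating center confirm severe TR on the baseline echocardiogram.
- **Follow-up measure.** Section 2.4 lists "Improvement in grades of tricuspid regurgitation as assessed by echocardiogram" under the lead-in "Besides the above formal secondary endpoints, we will monitor for the following throughout the trial". It is therefore neither a primary nor a formal secondary endpoint. No scale is named.
- **Cut-points.** Appendix A gives "Vena contracta: >7 mm is in favor of severe TR; <6mm - non-severe TR". Its PISA cut-points (EROA of at least 40 mm², or regurgitant volume of at least "45 mL suggestive of severe TR"), its inflow velocity limit and its 3D EROA limit each mark severe only.
- **Analysis.** Section 2.3 has change from baseline "evaluated using the McNemar matched pairs test for dichotomous variables", and by t-test or Wilcoxon signed rank test for continuous ones. It does not say which applies to TR.
- **Schedule.** Table 1 repeats echocardiography at 24 hours, 30 days, 6 months and 1 year.

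**The concern.** The item looks one way only, and it starts from a category that has nothing above it in the readable text. Three things follow for a summary by grade.

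1. Worsening from severe has no category to move into.
2. A large reduction that stays within severe counts as no change.
3. Random reading error close to the threshold can move a patient down a grade but never up, so noise can look only like benefit.

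At stake is whether the trial can say anything useful about degree of TR, which section 2.1 leaves open. Appendix A already obtains quantities that can move both ways, but none is named as the TR follow-up measure, so the choice of what to report is left until the data are in.

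**Working it through.** The documents give no effect size, standard deviation or power for change in TR, so there is no figure to reproduce. Steps 1 and 2 rest on the documents' cut-points and the sample size of up to 15. Steps 3 to 5 are illustrations on assumed inputs.

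**1. What a single cut-point does with change.** Suppose the grade followed one Appendix A cut-point. The baseline values are examples.
- EROA (severe at 40 mm² or more): 80 to 40 is 1 − 40/80 = 50% down and still severe; 100 to 40 is 60% down and still severe; 41 to 39 is 1 − 39/41 = 5% down and changes category.
- Regurgitant volume (severe at 45 mL or more): 90 to 45 is 50% down and still severe.
- Vena contracta (severe above 7 mm): 12 to 7.1 mm is 1 − 7.1/12 = 41% down in width, or 1 − (7.1/12)² = 65% in area if the orifice is circular, and still severe.

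**2. If severe versus non-severe were tested by exact McNemar.** With every baseline severe, the worsening cell is 0 by design. With b patients improved, the two-sided p = 2 × 0.5^b. For b = 5, p = 0.0625; for b = 6, p = 0.031. So 6 of 15 must improve, and the test can point only towards improvement.

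**3. Effect of the ceiling, simulated on EROA.** Assumed: true EROA normal with mean 60 and SD 20 mm²; entry and follow-up both graded at 40 mm²; reading-error SD 5, 10 or 15 mm².

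| True change | Recorded as no change | Recorded as improved | Recorded as worse |
|---|---|---|---|
| None | 87% to 96% | 4% to 13% (0.6 to 1.9 of 15 patients) | 0 |
| 30% fall | 62% to 66% | 34% to 38% | 0 |
| 30% rise | 96.0% to 99.8% | 0.2% to 4.0% | 0 |

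**4. Grade against width, simulated on vena contracta.** Assumed: n = 15; all baseline readings above 7 mm; between-patient SD 2 mm; reading-error SD 1 mm; a uniform true 25% reduction.

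| Assumed mean width | Share below 6 mm | McNemar power, improved = below 6 mm | McNemar power, 6–7 mm also non-severe | Paired t-test on width |
|---|---|---|---|---|
| 9 mm | 23% | about 11% | about 77% | over 99% |
| 10 mm | 15% | about 2% | about 40% | over 99% |
| 12 mm | 4% | about 0% | about 1% | over 99% |

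The McNemar figures turn largely on where the unassigned 6 to 7 mm band falls.

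**5. Limits of the continuous measure.** The last column of step 4 owes much to the uniform response.
- With mean 10 mm and an assumed 25-point SD in percentage response, paired-t power is about 90% at n = 15 and about 71% at n = 10. Ten is roughly the number of survivors under the 30% six-month mortality assumed in section 4.1.3 (15 × 0.7 = 10.5).
- With the same spread and a mean fall of only 10%, power is about 27% at n = 15.
- With no true change, selecting on width above 7 mm produces an apparent fall. At 1 mm reading error it is 0.24 to 0.08 mm for means of 8 to 10 mm. At 2 mm error and mean 8 mm it is about 0.8 mm, and the paired t-test rejects about 20% of the time.

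**The case against.** The strongest reply is that this is a loosely worded monitoring item in an exploratory study with no power analysis. Several parts of that reply stand.

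- **Status.** TR grade is outside the primary and formal secondary endpoints, and neither study objective concerns it. This stands, and it limits the weight of the point.
- **Worsening can be recorded.** A reader might infer that the trial cannot show TR getting worse. The documents do not support that. Appendix A obtains vena contracta width, EROA and regurgitant volume; Table 1 repeats the echocardiogram; section 2.3 allows paired analysis of continuous change and, with a mixed model, of repeated measures. Only the grade has the ceiling.
- **McNemar is not assigned to TR.** No section dichotomises TR, and the plural in section 2.4 suggests an ordinal scale. The McNemar figures describe one possible analysis. An ordinal scale would still have nothing above severe unless such a grade is defined.
- **Entry criteria are alternatives.** A patient may qualify through hepatic vein flow reversal with a vena contracta of 7 mm or less, and could later rise above 7 mm. This stands for the vena contracta cut-point, and step 4 does not cover such patients. They are still graded severe overall, so the ceiling on grade remains.
- **The cut-points are supportive signs.** Appendix A words them as favouring or suggesting severe TR, not as a grading rule. The examples in step 1 therefore show what a threshold does, not how a reader must grade. That no rule is stated is part of the gap.
- **The ceiling is an inference.** Figures are not shown and the cited echo guidance is not available here, so a higher grade might be defined there. None appears in the readable text.

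**Conclusion.** The stated measure has a ceiling at entry, looks in one direction and has no defined scale, while the continuous measurements that would answer the section 2.1 question are collected but not named for follow-up. This is a gap in specifying an exploratory item; no primary or formal secondary conclusion depends on it.

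The ceiling follows from the text, given that no grade above severe is defined elsewhere. The sizes do not. The 62% to 66% of true 30% falls missed, the 4% to 13% of spurious improvements and all the power figures rest on assumed means, SDs and reading errors.

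A reader might also infer that the continuous measures are free of these problems. They are not: selection on severity can produce regression to the mean in width, and the 6-month comparison covers survivors only. Their advantage is that they can show change in both directions and within severe.

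**What to change.** - In section 2.4, replace the improvement-in-grades item with change from baseline, in either direction, in vena contracta width, EROA and regurgitant volume, all already in Appendix A.
- Under section 2.3, report each as paired mean or median change with a 95% confidence interval, with the number of patients who have paired readings at each visit. Add a note that selecting on severity can produce some regression to the mean.
- Keep grade as a descriptive baseline-by-follow-up table without a significance test. State the scale used, including where 6 to 7 mm falls, and note that worsening beyond severe cannot be shown.

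The cost is wording only, with no new visit or procedure. The downsides are that some PISA-based values will be missing and that the 6-month change describes survivors.
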